### **4.3. Analysis of Primary Efficacy Endpoint**

Efficacy analyses will be conducted using the mITT population. The primary efficacy analyses will also be conducted on the PP population as a sensitivity analysis (See [Section 4.3.3](#)).

---

#### 4.3.1. Primary Efficacy Analyses

The primary endpoint of this study is the change from baseline in uPCR (Schedule A) on the natural log scale at Month 12 (Days 360) (See [Section 3.4](#) for change from baseline on the natural log scale equation).

A Mixed Model with Repeated Measurements (MMRM) will be used to compare the change from baseline in uPCR (Schedule A visits Months 9 and 12) on the natural log scale between treatment groups. The response variable of the MMRM is the change from baseline in uPCR (Schedule A) on the natural log scale. The model includes the fixed effects of treatment group, categorical visit (Months 9 and 12), strata and a treatment-by-visit interaction, with a fixed effect covariate of baseline uPCR (Schedule A) on natural log scale. An unstructured covariance matrix will be used. If the model does not converge, then the Toeplitz covariance structure will be used.

From the MMRM, the following statistics will be produced: 1) the least-square mean (LSM), its corresponding standard error (SE), and 95% confidence interval (CI) for each treatment group; 2) the geometric mean ratio calculated by exponentiated (LSM) and 95% CI for each treatment group; 3) the least-square mean difference (LSMD) between treatment groups using placebo as reference, its corresponding SE and 95% CI and p-value for testing the LSMD; and 4) the treatment difference expressed as geometric mean reduction calculated as  $(1 - \text{exponentiated LSMD}) \times 100\%$ , and 95% CI.

The geometric mean reduction and corresponding SE estimated from the MMRM for each treatment group will also be presented graphically.

The alpha value for the primary efficacy analyses (ie, p-value for the test of linear contrast at Month 12) will be adjusted to account for one review of the efficacy endpoint during the interim analyses. Although the interim efficacy data reviews will not include hypothesis testing ([Section 4.8.1](#)), the type I error rate for the primary endpoint will be reduced by 0.002 for the interim efficacy review, resulting in a 2-sided type I error rate of 0.048 for the linear contrast p-value. A p-value < 0.048 for the linear contrast of the primary efficacy analysis will support a claim of efficacy.

The primary efficacy analysis result also includes the p-value from the linear contrast statement of -3, -1, 1, and 3 evaluated for VIS649 dose levels 0 (placebo), 2, 4, and 8 mg/kg, respectively at Month 12.

In addition to the linear contrast for the primary efficacy result, a quadratic contrast statement of 0.56, -0.32, -0.64, and 0.40 will also be evaluated for VIS649 dose levels 0 (placebo), 2, 4, and 8 mg/kg, respectively at Month 12 as well as a cubic contrast statement of -0.28, 0.76, -0.57 and 0.09 for VIS649 dose levels 0 (placebo), 2, 4, and 8 mg/kg, respectively at Month 12. The quadratic and cubic weights are from an R orthogonal polynomial function (R, 2020).

In addition, pairwise comparisons between the treatment groups (placebo, 2, 4, and 8 mg/kg) using different dose level as reference will be performed at Month 12. The geometric mean reduction, corresponding SEs and 95% CI for testing treatment differences will be reported. The percent change in uPCR from baseline (ie,  $-1(\text{geometric mean ratio reduction})$ ) and

corresponding SE estimated from the primary MMRM for each treatment group will be presented graphically. The p-values of pairwise comparisons between all treatment groups will also be reported.

The baseline through Month 12 MMRM will be used to compare the change from baseline in uPCR (Schedule A) on the natural log scale between the pooled VIS649 and placebo. The outputs will be similar to those estimated from the MMRM for each individual treatment group.

uPCR (Schedule A) on the natural log scale and changes from baseline will be summarized descriptively by treatment group and visit, including number and percentage of participants with missing or incomplete assessments at that visit. The raw uPCR (Schedule A), and the ratio change from baseline over time, will also be summarized over time using the geometric mean ( $\pm$  95% CI).

uPCR (Schedule A and Schedule B) that is unable to be calculated because the total protein excretion is below the lower limit of quantification (LLOQ) will be reported in the statistical summaries as such. The LLOQ for the total protein excretion that is being used to calculate uPCR is [REDACTED]. To account for individual differences due to creatinine values, values that are below the limit of quantification (BLQ) will be calculated using the imputed total protein excretion value of [REDACTED], divided by the participant's urine creatinine level in mg/24h for that visit. These imputed values will be included in the calculation of descriptive statistics.

In addition, the raw spot uPCR (Schedule B), and the ratio change from baseline will be summarized over time using the geometric mean ( $\pm$  95% CI).

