	
be stratified by screening uPCR (≤ 2.0 g/g vs > 2.0 g/g).
 
Interim Analysis
 
In addition to 5 DSMB safety reviews, 3 interim PK/Ig analyses and 1 interim efficacy analysis are planned. The interim PK/Ig analyses will provide additional data for population PK/PD modeling and will advise the study Sponsor on future study design and planning.
 
An interim efficacy analysis will be performed at the time of the fourth scheduled DSMB meeting (when 50% of randomized participants have completed the Month 6 visit reflecting 6 months of study intervention or placebo exposure and ~ 20 participants have completed 12 months of dosing). Group-unblinded efficacy summaries (with individual participant treatment blinded) will be prepared for Sponsor review to inform future study design.
 
The interim efficacy analysis will not include hypothesis testing and will be for the purpose of future study design and planning. The primary efficacy endpoint, change in proteinuria from baseline, will be analyzed. No modifications to this study protocol are planned based on results of the interim analyses.
 
Planned analyses
 
The primary efficacy outcome for this study is the change from baseline in uPCR on the natural log scale at Month 12. Dose response will be explored using orthogonal contrasts. Sensitivity analysis will follow using dose as a continuous covariate with associated linear, quadratic, and cubic terms.
 
In addition, to assess the dose response over time, a Mixed Model with Repeated Measurements (MMRM) which includes fixed class-effects of treatment, visit, randomization strata, and treatment by visit interaction, with a fixed effect covariate of baseline uPCR on the natural log scale will be used. An unstructured variance covariance matrix will be assumed, and linear, quadratic, and cubic dose responses will be assessed.
 
Secondary efficacy endpoints will be summarized using descriptive statistics. In addition, comparisons between dose groups against placebo will be performed using Analysis of Covariance or MMRM for continuous measures and logistic regression or generalized estimating equations for categorical variables.
 
Safety will be assessed by evaluation of AEs (including hypersensitivity reaction and anaphylactic reaction), physical examinations, injection site tolerability (including pain, irritation and tissue damage), clinical laboratory assessments (including biochemistry, hematology, and urinalysis), laboratory testing including serum Ig levels, vital signs, and concomitant medications.
 
Analysis of PK parameters will include participant data-listings of serum concentrations and summary statistics by group including means, geometric means, standard deviations, %CV, medians, and ranges, as appropriate. Summary graphs including mean concentration-time profiles by group will also be presented. For the subset of participants for whom intensive PK samples are collected, serum concentration data will be analyzed by [REDACTED].
 
[REDACTED]. In addition, [REDACTED].

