9.2 Sample Size Determination

A sample size of 144 participants, randomly assigned in a 1:1:1:1 schema to VIS649 2, 4, or 8 mg/kg, or placebo, would provide sufficient power at 80% to detect a significant linear dose response relationship given a standard deviation of 0.49, and an assumed difference in uPCR reduction, for instance 15%, 30%, and 45%, between VIS649 2, 4, or 8 mg/kg and placebo, respectively. The study-wide type I error rate is a 2-sided alpha of 0.05. This sample size would account for a dropout rate of ~20%.

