9.4.5.1 Primary Endpoint

The primary efficacy outcome for this study is the change from baseline in uPCR on the natural log scale at Month 12. Dose response will be assessed using orthogonal contrasts. Sensitivity analysis will be performed using dose as a continuous covariate with associated linear, quadratic, and cubic terms.

In addition, to assess the dose response over time, a Mixed Model with Repeated Measurements (MMRM) including fixed class-effects of treatment, visit, strata factors, and treatment by visit interaction, and a fixed effect covariate of baseline uPCR on the natural log scale will be used.

An unstructured variance covariance matrix will be assumed, and liner, quadratic, and cubic dose responses will be assessed.

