### **3. GENERAL STATISTICAL METHODS**

#### **3.1. Sample Size Justification**

The sample size for this study was calculated assuming a linear dose response (reduction of uPCR) of 0%, 15%, 30%, and 45% in placebo and VIS649 2, 4, and 8 mg/kg groups, respectively. Applying contrasts of -3, -1, 1, and 3 for the corresponding dose levels and analyzing uPCR on the natural log scale, the result is an expected mean change from baseline of 0, -0.163, -0.357, and -0.593 for placebo and VIS649 groups of 2, 4, and 8 mg/kg, respectively. Using an analysis of variance model with contrasts of -3, -1, 1, and 3 for the corresponding groups, a standard deviation (SD) of 0.87, 80% power, a 2-sided type I error rate of 0.05, and accounting for a dropout rate of ~ 20%, the required sample size is 36 participants per group, or 144 participants overall.

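### The linear contrast uses equal steps but the quadratic and cubic use mg/kg spacing, so the Month 12 set is not orthogonal as the protocol specifies (minor)

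*SAP*

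**What the plan says.** Protocol 9.4.5.1 says of the Month 12 endpoint: "Dose response will be assessed using orthogonal contrasts". The synopsis has the same requirement: "Dose response will be explored using orthogonal contrasts". Neither names a dose scale. Protocol 9.4.5.1 also plans a check on the mg/kg scale: "Sensitivity analysis will be performed using dose as a continuous covariate with associated linear, quadratic, and cubic terms".

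SAP 4.3.1 makes the primary result the p-value from the "linear contrast statement of -3, -1, 1, and 3 evaluated for VIS649 dose levels 0 (placebo), 2, 4, and 8 mg/kg". A p-value below 0.048 on that contrast alone supports the efficacy claim. The SAP then says that "a quadratic contrast statement of 0.56, -0.32, -0.64, and 0.40 will also be evaluated" for the same four dose levels, with a cubic of -0.28, 0.76, -0.57, 0.09. It gives a source for these two only: "The quadratic and cubic weights are from an R orthogonal polynomial function (R, 2020"). It does not say that the linear weights rest on a different spacing, and SAP Section 5 does not list this as a change from the protocol.

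**The concern.** The weights -3, -1, 1, 3 are the linear polynomial for four equally spaced levels. The doses 0, 2, 4, 8 mg/kg are not equally spaced, and the quadratic and cubic weights look as if they were computed for those doses. An orthogonal polynomial set has to use one scale throughout, whichever scale is chosen.

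If the scales are mixed, the quadratic and cubic do not test departure from the trend that the primary contrast evaluates. Each is a valid test of a different null, namely no curvature per mg/kg. A reader who sees a linear and a quadratic p-value side by side will normally take the second as a check on the first. In a phase 2 trial whose primary efficacy objective is dose response, that reading could give the curvature the wrong direction.

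**Working it through.** **Inputs.** The contrast weights are from SAP 4.3.1. The planning means on the log scale are from SAP 3.1: "expected mean change from baseline of 0, -0.163, -0.357, and -0.593 for placebo and VIS649 groups of 2, 4, and 8 mg/kg". The SD is 0.87 in SAP 3.1, and Protocol 9.2 gives another value ("given a standard deviation of 0.49"), so both are shown. There are 36 per group less 20% dropout, so n = 28.8 per group and df = 4 × 28.8 - 4 = 111.2.

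**1. Reproduce the SAP weights.** Centring 0, 2, 4, 8 at 3.5 and doubling gives the mg/kg linear weights -7, -3, 1, 9. Their orthogonal partners, divided by their lengths, are:
- quadratic 7, -4, -8, 5 over √154: 0.564, -0.322, -0.645, 0.403
- cubic -3, 8, -6, 1 over √110: -0.286, 0.763, -0.572, 0.095

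Cut to two decimals, these are the SAP's quadratic and cubic weights, so both are coded for actual dose.

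**2. Test orthogonality with the SAP's linear contrast.** The cosine is a·b / √(a·a × b·b). With equal groups and variances it is the correlation of the two estimates.
- Linear × quadratic: (-3)(0.56) + (-1)(-0.32) + (1)(-0.64) + (3)(0.40) = -0.80. Cosine = -0.80 / √(20 × 0.9856) = -0.180. The exact integers 7, -4, -8, 5 also give -0.180, so rounding is not the cause.
- Linear × cubic: (-3)(-0.28) + (-1)(0.76) + (1)(-0.57) + (3)(0.09) = -0.22. Cosine = -0.22 / √(20 × 0.989) = -0.049.
- For comparison, -7, -3, 1, 9 with the SAP quadratic: -3.92 + 0.96 - 0.64 + 3.60 = 0.

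**3. Direction of curvature under the SAP 3.1 means.**
- Steps between adjacent groups: 0.163, 0.194, 0.236. They steepen, and the equal-step quadratic 1, -1, -1, 1 gives 0.163 + 0.357 - 0.593 = -0.073.
- Steps per mg/kg: 0.163/2 = 0.082, 0.194/2 = 0.097, 0.236/4 = 0.059. They flatten at the top, and the SAP quadratic gives (-0.32)(-0.163) + (-0.64)(-0.357) + (0.40)(-0.593) = +0.043.

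**4. Shares of the between-group sum of squares.** Each share is (c·m)² / (c·c) divided by Σ(m - m̄)² = 0.19598. The SAP set gives 99.32% + 0.98% + 0.36%, which is 100.65% from unrounded shares. Either complete orthogonal set gives 100%.

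**5. Rejection rates.** These use the noncentral t with noncentrality c·m / (SD × √(c·c / n)), two-sided 0.05.

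| Assumed means | Quadratic | SD 0.87 | SD 0.49 |
|---|---|---|---|
| SAP 3.1 | SAP | 5.8% | 7.6% |
| SAP 3.1 | equal-step | 5.6% | 6.8% |
| Equal-step linear (0, -0.2, -0.4, -0.6) | SAP | 7.8% | 14.1% |
| Equal-step linear | equal-step | 5.0% | 5.0% |
| mg/kg linear (0, -0.15, -0.30, -0.60) | SAP | 5.0% | 5.0% |
| mg/kg linear | equal-step | 7.4% | 12.9% |

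Under SAP 3.1 at SD 0.87 the quadratic noncentralities are +0.27 (SAP) and -0.23 (equal-step). The second and third sets of means are assumptions made for illustration. The 7.8% and 14.1% reflect real curvature in mg/kg and are not false-positive rates.

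**6. Primary test.** With the SAP 3.1 means, SD 0.87 and alpha 0.048, power is 76.4% with -3, -1, 1, 3 and 76.2% with -7, -3, 1, 9.

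**The case against.** The arithmetic is not in dispute. The case against acting on it has four parts.

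- **No decision changes.** The efficacy claim rests on the linear contrast alone, which sums to zero and matches the contrast used for sizing. The least-squares means, pairwise comparisons and plot show the shape directly. This stands, and it is why the point is minor.
- **The protocol text can be read more loosely.** Protocol 9.4.5.1 attaches orthogonality to the Month 12 analysis and introduces the repeated-measures model separately, asking there only that the three dose responses be assessed. But the SAP contrasts are evaluated at Month 12 and serve the primary endpoint, so the requirement reasonably applies to them.
- **Exact orthogonality will not hold anyway.** With unequal completers, strata and a baseline covariate, the estimates will be correlated. For example, with assumed completers of 36, 33, 30 and 24, the pair -3, -1, 1, 3 and 1, -1, -1, 1 has correlation Σ(ab/n) / √(Σ(a²/n) × Σ(b²/n)) = 0.0386 / √(0.6886 × 0.1331), about 0.13. This is true, but it does not excuse weights that fail even with equal groups. The null that each contrast tests is fixed by its weights, whatever the group sizes.
- **The planning mean for the top dose is slightly off.** ln(0.55) is -0.598, not -0.593. With -0.598 the two quadratics become about +0.041 and -0.078. The signs stay opposite.

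It is also fair that neither quadratic is free of a scale: the equal-step version has the mirror-image limitation shown in the table. That is a reason to name the scale of each set.

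**Conclusion.** The point holds. The SAP combines an equal-step linear contrast with mg/kg quadratic and cubic contrasts, so the set is not orthogonal as the protocol specifies, and the SAP does not disclose the mix. The severity is minor. The primary test, its 0.048 alpha and its power are unaffected, and the shape tests carry no alpha and no decision rule. What is lost is interpretation: the reported quadratic does not measure departure from the primary trend, and under the SAP's own planning means it has the opposite sign to the one that does. One trial would rarely tell the two apart.

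The weights and dot products are exact arithmetic. The rejection rates assume a simple analysis of variance with 28.8 per group and a common SD of 0.87 or 0.49, and the repeated-measures model will differ slightly.

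**What to change.** 1. Keep the primary contrast -3, -1, 1, 3 and the 0.048 alpha. Label it as a trend across ordered dose groups in equal steps.
2. Use its own partners as the shape tests for that trend: quadratic 1, -1, -1, 1 and cubic -1, 3, -3, 1.
3. Keep the mg/kg weights as a complete, separately labelled supportive block in exact integers: linear -7, -3, 1, 9; quadratic 7, -4, -8, 5; cubic -3, 8, -6, 1. With equal groups these correspond to the linear, quadratic and cubic dose terms entered in sequence. The block therefore covers the scale of the protocol's continuous-dose sensitivity analysis, which is not among the three in SAP 4.3.3.
4. State the dose scale of each set. Note that neither quadratic is scale-free, and that in the repeated-measures model orthogonal weights give only approximately uncorrelated estimates.
5. Record the change and its reason, with a date, in SAP Section 5, because the sponsor has already seen group-level interim results.

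Switching the primary contrast to -7, -3, 1, 9 would also restore orthogonality, but it would alter the primary test after that interim look and is not advised.

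The cost is two contrast lines, one supportive block, the labels and the Section 5 entry. The shape p-values change; the primary test, alpha and sample size do not.

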### **3.7. Multiple Comparisons/Multiplicity**

Formal statistical hypothesis testing will be performed on the primary efficacy endpoint of linear dose response in change from baseline in uPCR on the natural log scale at Month 12, conducted at the 2-sided, 0.048 level of significance to preserve the study-wide 2-sided type I error rate at 0.05 while accounting for interim data review ([Section 4.8](#)). The inclusion of statistical tests for secondary endpoints is intended to yield supportive evidence related to the primary objective and will be descriptive in nature as no confirmatory conclusions are intended. Statistically significant results will be examined in sequence from high dose (8 mg/kg) to low dose (2 mg/kg) compared with placebo. Tests of probability are not planned for the exploratory endpoints so that multiplicity of statistical probability test results is not a consideration.

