### **3.10. Missing Data**

In general, there will be no imputation performed for missing data, including efficacy, safety, PK, PD, and ADA, unless otherwise specified. All data recorded on the case report form will be included in data listings that will accompany the CSR.

Missing data due to discontinuation of treatment, withdrawal from the trial or missed endpoint ascertainment will be reported at the subject level with a description of the context and/or reason for the missing data (eg, 'COVID-19').

For the primary efficacy endpoint, if a result is missing or not evaluable for 24-hour uPCR, and there is an unscheduled visit within 30 calendar days of the nominal visit date, the unscheduled visit assessment will be treated as the nominal timepoint.

For the analysis of AE, only partial dates will be imputed unless otherwise specified. The algorithms for imputation of partial dates depend upon the parameter, as follows:

- If the day of the month is missing, the onset day will be set to the first day of the month unless it is the same month and year as study treatment. In this case, in order to conservatively report the event as treatment-emergent, the onset date will be assumed to be the date of treatment.
- If the onset day and month are both missing, the day and month will be assumed to be January 1, unless the event occurred in the same year as the study treatment. In this case, the event onset will be coded to the day of treatment to conservatively report the event as treatment-emergent.
- A missing onset date will be coded as the day of treatment.

Adverse events with missing relation will be considered related. Adverse events with missing severity will be considered severe.

For the analysis of concomitant medication, incomplete start/stop dates will be imputed based on the following imputation rules:

- If start date is completely missing, start date will not be imputed.
- If start year is present and month and day are missing, or year and day are present and month is missing, set start month and day to January 1.
- If start year and month are present and day is missing, set start day to 1st day of the month.
- If end date is completely missing, end date will not be imputed.
- If end year is present and month and day are missing, or year and day are present and month is missing, set end month and day to December 31.
- If end year and month are present and day is missing, set end day to last day of the month.

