#### 4.4.1.2. 24-hour Urine Protein Excretion

The MMRMs will be fitted to estimate the treatment difference for the 24-hour urine protein excretion at Months 9, 12, and 16, respectively. Since the distribution of 24-hour urine protein excretion is skewed, the response variable will be the natural log transformed ratio of 24-hour urine protein excretion. The models will include the treatment group, strata, categorical visit, treatment-by-visit, and natural log transformed baseline 24-hour urine protein excretion as covariates. The model for Months 9 and 12 will include Baseline, Months 9 and 12. The model for Month 16 will include Baseline, Months 9, 12 and 16. The treatment differences on these assessments at Months 9, 12, and 16 will be estimated from their respective models by the differences in the geometric mean ratio reduction, along with the SEs, 95% CIs, and p-values.

24-hour Urine Protein Excretion that is unable to be calculated because the total protein excretion is below the lower limit of quantification (LLOQ) will be noted in the associated listing as such. Statistical summary tables that include imputed values will be indicated in the footnotes. The LLOQ for this test is [REDACTED]. Values that are below the limit of quantification (BLQ) will be substituted with [REDACTED] for the statistical summaries and the calculation of descriptive statistics.

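### The SAP does not say whether substituted values for protein results below the quantification limit enter the primary MMRM, and its substitution rule cannot be applied to spot urine

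*SAP*

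**What the plan says.** SAP 4.3.1 defines the primary analysis as an MMRM on the log change from baseline in Schedule A uPCR at Months 9 and 12, with a linear contrast (-3, -1, 1, 3) tested at Month 12. That specification does not mention results below the quantification limit.

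Later in 4.3.1, straight after the paragraph on descriptive summaries, the SAP covers a uPCR that cannot be derived because protein is below the limit. It is reported as such, and a value is computed from a substituted protein amount (redacted) divided by the participant's urine creatinine in mg/24h at that visit. The paragraph ends: "These imputed values will be included in the calculation of descriptive statistics". The rule is stated for both Schedule A and Schedule B.

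For 24-hour protein excretion, SAP 4.4.1.2 substitutes a value "for the statistical summaries and the calculation of descriptive statistics". SAP 3.10 sets the default: "In general, there will be no imputation performed for missing data, including efficacy, safety, PK, PD, and ADA, unless otherwise specified". The ANCOVA in 4.3.3 and the responder models in 4.4.1.6 say nothing on BLQ results.

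SAP 1.2.1 describes Schedule B as spot collection. Protocol Table 1 schedules 24-hour collections only at screening, Month 9, Month 12 and end of study.

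**The concern.** A BLQ protein result is the most favourable value a participant can have, and it becomes more likely as the drug works better. If an analysis data set treats it as missing because the substituted value was provided only for summaries, the analysis rule itself removes the best outcomes. It removes more of them from the effective doses than from placebo. The MMRM's missing-at-random assumption does not cover this, since the value is missing because of its own size.

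The primary test is a linear dose contrast with the largest weights on placebo and 8 mg/kg, so the loss would flatten the quantity being tested. The same omission could leave participants uncounted in the ≥30% uPCR responder analysis. Two programmers following the current text could reach different primary p-values.

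The Schedule B defect does not depend on how the text is read: the stated divisor does not exist for a spot sample.

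**Working it through.** **Inputs.** SAP 3.1 gives the "expected mean change from baseline of 0, -0.163, -0.357, and -0.593 for placebo and VIS649 groups of 2, 4, and 8 mg/kg", with "a standard deviation (SD) of 0.87". The protocol's sample size section instead works "given a standard deviation of 0.49", so both SDs are carried. Sizing uses "80% power, a 2-sided type I error rate of 0.05"; the final test is "conducted at the 2-sided, 0.048 level of significance to preserve the study-wide 2-sided type I error rate at 0.05". The BLQ shares and the Month 9/12 correlation are assumptions.

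**1. The plan's own figure.** L = (-3)(0) + (-1)(-0.163) + (1)(-0.357) + (3)(-0.593) = -1.973. Evaluable n per group = 20 × [SD × (1.960 + 0.842) / L]² = 20 × [0.87 × 2.802 / 1.973]² = 30.5. Multiplying by 1.2 for dropout gives 36.6, close to the stated 36; with ln 0.55 = -0.598 for the top dose it is 30.07 × 1.2 = 36.09. The setup therefore matches the SAP's.

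**2. One visit, BLQ values dropped.** Set a common threshold t so that a share p of the 8 mg/kg arm lies below it: t = -0.593 + SD × z_p. In each arm with mean μ, put z = (t - μ)/SD and P = Φ(z); the mean of the retained values rises by SD × φ(z)/(1 - P).

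Example with p = 5% and SD 0.87: t = -0.593 - 1.645 × 0.87 = -2.024, or 0.132 of baseline. BLQ shares are 1.0%, 1.6%, 2.8% and 5.0% from placebo to 8 mg/kg, and the mean shifts are 0.0234, 0.0358, 0.0569 and 0.0945. The contrast changes by 3 × (0.0945 - 0.0234) + (0.0569 - 0.0358) = 0.234, giving -1.739, a shrinkage of 0.234/1.973 = 11.9%. The 8 mg/kg reduction against placebo falls from 1 - exp(-0.593) = 44.7% to 40.7%.

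| BLQ at 8 mg/kg | Threshold / baseline | BLQ on placebo | Contrast | Shrinkage | 8 mg/kg vs placebo | Approx. power |
|---|---|---|---|---|---|---|
| none | – | – | -1.973 | – | 44.7% | 0.774 |
| 1% | 0.073 | 0.1% | -1.909 | 3.3% | 43.6% | 0.759 |
| 2% | 0.093 | 0.3% | -1.859 | 5.8% | 42.8% | 0.745 |
| 5% | 0.132 | 1.0% | -1.739 | 11.9% | 40.7% | 0.708 |
| 10% | 0.181 | 2.5% | -1.583 | 19.7% | 37.8% | 0.650 |

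Power is a normal approximation at two-sided 0.048 with 29 evaluable per group (36 × 0.8 = 28.8), using the reduced group sizes and the smaller SD of the retained values.

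**3. Two visits, as in the MMRM.** A participant who is BLQ at Month 12 but quantifiable at Month 9 stays in the model, which recovers part of the loss. Maximum likelihood on large simulated samples, with equal means at both visits and correlation 0.5 to 0.8, gives this contrast shrinkage:

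| BLQ at 8 mg/kg | SD 0.87 | SD 0.49 |
|---|---|---|
| 2% | 3–4% | 2–3% |
| 5% | about 10% | 6–7% |
| 10% | 17–19% | 12–13% |

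**4. BLQ values included instead.** Over the same scenarios, substituting at the limit shrinks the contrast by 0–6%; substituting at half the limit enlarges it by about 1–8%. Inclusion reduces the distortion in each scenario, but the substituted value still matters somewhat.

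**5. Schedule B.** The rule needs creatinine in mg/24h at the same visit. Schedule B visits are Day 1, Day 8 and the monthly visits other than Months 9 and 12; Protocol Table 1 lists no 24-hour collection at any of them. The rule therefore cannot be executed for the Schedule B summaries in 4.3.1 or for Sensitivity Analysis 2 in 4.3.3, which repeats the primary analysis on Schedule B data.

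**The case against.** The strongest reply is that the SAP never confines the substituted values to descriptive output. The rule sits in the primary efficacy section and defines how uPCR itself is calculated. Its closing sentence is inclusive, and the revision history for version 5.0 records the addition without restriction. Section 3.10 speaks of missing data and yields to anything otherwise specified, while a BLQ result is an observed low value. Where the authors want such values set to missing they say so, as for post-peak PK concentrations in 4.6.2.

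This stands to the extent that a reader may not infer that BLQ results will be dropped; inclusion is an open reading. It does not settle the matter. Sections 4.6.1 and 4.6.2 give different BLQ rules for descriptive statistics and for PK evaluation, so this SAP treats those as separate uses, and no sentence names the MMRM.

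A reader might also infer that remitters are lost from the <300 mg/day endpoint. No text excludes BLQ results there, and if the limit is below 300 mg/day such a result meets the criterion without any substituted number.

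The sizes above are scenarios, as the reply would rightly say. Quantification depends on absolute protein rather than change from baseline, so removing exactly the largest falls is close to a worst case. The 10% scenario at SD 0.87 requires protein below 0.181 of baseline: about 181 mg/day from 1.0 g/day, or 362 mg/day from an assumed 2 g/day. For many participants that needs a limit near or above the remission cut-off.

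**Conclusion.** The point holds as an unstated choice that could affect the primary result, together with one rule that cannot be carried out as written. If BLQ values were excluded, the bias would run toward zero, and at SD 0.87 the two-visit contrast would shrink by about 3–4%, 10% and 17–19% at assumed BLQ shares of 2%, 5% and 10% at 8 mg/kg. At 1–2% the loss is small: one-visit power moves from about 0.77 to between 0.745 and 0.76. These figures rest on normal log changes, a common threshold relative to baseline, and Month 9/12 correlations of 0.5 to 0.8. The redaction of the limit is not a defect; it only prevents a firmer estimate.

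SAP Section 5 records that the document was amended after the interim efficacy analysis, with the sponsor aware of group-level results. A reader might infer that the BLQ rule was shaped by those results; nothing in the documents shows that. It is a reason to put the choice in writing rather than leave it to programming.

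The change should be made, but it does not put the design in question.

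**What to change.** In SAP 4.3.1 and 4.4.1.2, state that BLQ-substituted uPCR and 24-hour protein values enter the MMRMs and the ANCOVA in 4.3.3 as well as the summaries. In 4.4.1.6, state that they enter the responder definitions, with a BLQ protein result counted as <300 mg/day if the limit is below that value. For Schedule B, divide the substituted protein concentration by the spot creatinine concentration. Optionally, add one sensitivity analysis of the primary endpoint treating BLQ values as left-censored, since the substituted value is somewhat arbitrary.

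The cost is about a sentence per section and, if adopted, one extra model run. No new data are needed.
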